### COPD Exacerbation

- COPD subjects will be asked for a history of AECOPD using components of moderate/severe exacerbation definition at each clinic visit including exacerbation visits.
- Additionally, COPD subjects will be contacted by phone every 3 months by the study staff and asked about their exacerbation details for the previous 3 months.
- Study staff will check Hospital Information System (HIS) during the interview to confirm the event of exacerbation wherever possible.

### Digital Physical Activity

- Daily physical activity will be collected in sub-cohort only. Participants are required to keep wearing the wrist band for 1 month from visit 1 and 3 as outlined in the time and event table ([Appendix 2: Schedule of Activities](#)).
- Daily activity as measured by number of daily steps will be captured using digital mobility devices (wrist bands) worn by participants, dispensed at baseline.
- Daily steps walked, sedentary minutes, active minutes, very active minutes, sedentary minutes and total sleeping minutes will be derived and summarized.
- Definition of intensity data

**Digital Physical Activity**

- SEDENTARY - Little to no activity monitored. This could be due to minimal movement, sitting, resting, or sleeping.
- ACTIVE - Some activity monitored. A brisk walk could achieve this intensity.
- HIGHLY\_ACTIVE - High activity monitored. Running or speed walking could achieve this intensity.

• Below is a template of how activity information is summarized for site personnel in Rave EDC

CRF Component	Value Format	Calculation	Example Values
Date	Text	Date of log line record	26 MAR 2015
Sync Date/Time	Text	Date and time data was synced to Garmin	26 MAR 2015 14:00
Daily Steps Walked	Numeric	Total # of steps in routine data objects for a subject's day (timezone is subject's)	2240
Sedentary Minutes	Numeric	Total # of minutes in routine data objects for a subject's day (timezone is subject's) with intensity parameter = sedentary	438
% of time sedentary	Numeric	Total # of minutes in routine data objects for a subject's day (timezone is subject's) with intensity parameter = sedentary divided by 1440 minutes (total # of minutes per day)	85.32
Active Minutes	Numeric	Total # of minutes in routine data objects for a subject's day (timezone is subject's) with intensity parameter = active	74
% of time active	Numeric	Total # of minutes in routine data objects for a subject's day (timezone is subject's) with intensity parameter = active divided by 1440 minutes (total # of minutes per day)	14.47
Very Active Minutes	Numeric	Total # of minutes in routine data objects for a subject's day (timezone is subject's) with intensity parameter = very active	1
% of time very active	Numeric	Total # of minutes in routine data objects for a subject's day (timezone is subject's) with intensity parameter = very active divided by 1440 minutes (total # of minutes per day)	0.20

Digital Physical Activity			
Total Daily Minutes Sleep	Numeric	Total # of minutes in sleep data objects for a subject's day (timezone is subject's)	362

Phenotype	
Exacerbator	

 
Exacerbator is categorized based on the number of exacerbations patients have in the past:           
 
Never
 
Occasional (1 in the last 2 years)
 
Yearly (1 each year in the last 2 years)
 
 
 
Frequent (<math>\geq 2</math> in the previous year)
 
	
Chronic mucus hypersecretion (CMH)	

 
Chronic mucus hypersecretion (CMH) is defined as: At least 3 months of cough & phlegm in past year. This will be identified by asking a question as "How many months in the past 12 months have you had bronchitis or chronic coughing with phlegm or sputum from the chest?"
 
SGRQ-C will be used for identification of CMH in this study. This would be identified by cough and phlegm related questions in SGRQ-C or CAT.
 
SGRQ-CMH is defined by answering cough for most days or several days a week (option 1 or 2 for the "I cough" question) and phlegm for most days or several days a week (option 1 or 2 for the "I bring up phlegm [sputum]" question) (Kim et al. 2021)
 
Significant Symptoms is defined as a CAT score of 10 or higher.
 
	
Significant Symptoms	

 
Significant Symptoms is defined as scoring 10 or higher in the CAT questionnaire.
 
	
Asthma-COPD Overlap (ACO)	

 
Asthma-COPD overlap (ACO) has been used to identify patients with airway disease who have features of both asthma and COPD.
 
ACO is defined as COPD patients that have physician diagnosed asthma <math>\leq 40</math> years of age
 
	

Endotype	
Airflow Limitation	

 
FEV1 (GOLD grade)
 
	
PRISM	

 
Normal FEV1/FVC ratio, but FEV1 <math>< 80\%</math> pred
 
	
'Pure' Airways Disease	

 
Airway wall thickening on CT
 
No emphysema on CT
 
	
Presence of emphysema	

 
CT scan – standard definition now available
 
	

Higher Blood Eosinophils
• Eosinophils > 300 $\mu$ l
Fibrinogen
• Plasma fibrinogen > 400 mg/dL

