**Figure 3 Sub-cohort Population Schematic**

For subjects included in COPD groups, Non-exacerbator is defined as a patient who has not had an exacerbation (see definition of exacerbation below) in the 2 years before entry into the study; Exacerbator is a patient who has 1 or more exacerbations in the 2 years before recruitment. In this study, an exacerbation is defined by the occurrence of an episode of increased cough (with or without phlegm), shortness of breath or chest symptoms (chest discomfort or tightness) which lasted 48 hours or more and interfered with the participant's usual activities (with or without treatment).

Inhaled maintenance treatment naïve patients will be defined as not being treated in at least prior 12 months with any long-acting inhaled medications inclusive of inhaled corticosteroids, long-acting antimuscarinic or long-acting beta2-agonists.

To minimize selection bias, study investigators are encouraged to follow their routine clinical practice and consecutively recruit all eligible patients at their practice. The investigator will maintain a screening log to collect details (e.g. age, sex, smoking status, presence of chronic mucus hypersecretion (CMH) and maintenance inhaler treatment) of all participants screened, to confirm eligibility, and to record reasons for study exclusion, as applicable. Recruitment process will be closely monitored to ensure the proper number of participants within each subgroup. A patient informed consent will be obtained from all participants to allow their past, current and follow-up period information to be collected and used. Sub-cohort participants are required to provide a separate consent for additional assessments.

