### 6.1. Inclusion Criteria

#### COPD Participants

A COPD subject will be eligible for inclusion in this study only if all the following criteria apply:

1. Male or female participants, aged 40-80 years inclusive.

A female is eligible to enter and participate in the study if she is of non-child bearing potential.

2. A baseline (post-bronchodilator) FEV1/FVC ratio  $<0.70$

3. Clinically stable and has no exacerbations for at least 1 month prior to recruitment.  
All courses of oral corticosteroids or antibiotics must be completed at least 2 weeks before study start.

4. Ever smoker (with a lifetime exposure of  $\geq 1$  pack-year) or never smoker (with a lifetime exposure of  $<1$  pack-year)

5. A signed and dated written informed consent is obtained prior to participation

6. Additional criteria for sub-cohort COPD participants to be recruited:

- Only include participants aged 50-80 years (inclusive)
- $BMI < 35 \text{ kg/m}^2$

- Only include ever smoker with a lifetime exposure of  $\geq 10$  pack-year or never smoker with a lifetime exposure of  $<1$  pack-year
- About 150 COPD participants with a history of at least 1 exacerbation event(s) within the past 2 years at the entry of the study
- About 60 COPD participants without inhaler maintenance treatment history for at least 12 months prior to the entry of the study (including inhaled corticosteroids, inhaled long-acting antimuscarinics, and inhaled long-acting beta2-agonists).

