### 9.1. Baseline data collection

A specifically designed baseline survey will be used to collect the following information at baseline from all participants, including:

Informed consent

Inclusion/exclusion criteria assessment

Socio-demographics

- Age
- Race/ethnicity
- Gender
- Education
- Economic status
- Occupation
- Insurance information (basic, commercial)

Health and lifestyle information

- Height, weight, body mass index (BMI)
- Blood pressure, heart rate
- Smoking status: Never smokers are defined as those with a lifetime exposure of <1 package/year in their life (excluding passive smoker). Ever smokers (current or former) are defined as those with a lifetime exposure of ≥10 package/year.

Former smokers are those who have stopped smoking for at least 6 months.

Current smokers are those who are currently smoking. Passive smokers are

defined as those with the presence of smokers living in the same household, or co-workers smoking nearby while indoors

- Smoking history including Pack-years of smoking: Number of pack years = (number of cigarettes per day / 20) x number of years smoked, e.g., 10 pack-years means 20 cigarettes per day for 10 years, or 10 cigarettes per day for 20 years)
- Biomass exposure: refer to the biomass exposure questionnaire
- Occupational exposures: Whether had the participant worked in occupations known or suspected to be associated with the risk of COPD  $\geq 6$  months, e.g. organic/inorganic dust, irritant gases, fumes, or vapors chef, traffic police Toxic and harmful jobs (eg.in pollution factory or chemical work, etc)

COPD Medical history (for COPD participants only)

- Disease duration
- Treatment history (e.g. the time of initiating maintenance treatment, current treatment)
- Number of exacerbations in the previous 12 months and 24 months
- Number of moderate and severe exacerbations in the previous 12 months and 24 months and their management with oral corticosteroids and/or antibiotics and/or hospitalization
- Family history of COPD or other respiratory diseases

Lower respiratory infections including chest colds (for chronic bronchitis patients only)

Medical history (including previous asthma history)

Current co-morbid conditions and childhood respiratory disease

Concomitant medications: Respiratory medications, antibiotics, oral steroids, anti-diabetic, anti-hypertension gastroesophageal reflux disease (GERD) therapy, cardiovascular disease therapy and whether taking traditional Chinese medicines

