### 13.1. Phenotypes

Summary of phenotypes in Full and Sub-cohort Population will be provided totally and by GOLD grades, including exacerbator, CMH, significant symptoms and ACO. The summary of phenotype will be performed in COPD patients.

- Exacerbator will be summarized with the following grades: Never, Occasional (1 in previous years), Yearly (1 each year in previous years) and Frequent ( $\geq 2$  more in previous year).
- CMH (Chronic Mucus Hypersecretion) is identified using the SGRQ-C questionnaire, defined by answering cough for most days or several days a week (option 1 **OR** 2 for the “I cough” question) **AND** phlegm for most days or several days a week (option 1 **OR** 2 for the “I bring up phlegm (sputum)” question).
- Significant symptoms will be summarized by CAT score  $\geq 10$  and  $< 10$ .
- ACO is defined as COPD patients that have physician diagnosed asthma  $\leq 40$  years of age. Status of ACO before the age of 18 and between age of 18 and 40 will be provided.

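### The exacerbator phenotype rows in the SAP are not exhaustive: COPD patients with 2 or more exacerbations in the year before last and 0 or 1 last year fit no row

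*SAP*

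**What the plan says.** SAP 17.5.3 (Phenotype, Exacerbator) opens with "Exacerbator is categorized based on the number of exacerbations patients have in the past". It then lists Never, "Occasional (1 in the last 2 years", "Yearly (1 each year in the last 2 years", and Frequent, which needs at least two "in the previous year". The RAP bound into the same file has the same list in its section 12.5.3.

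SAP 13.1 names the same grades more loosely, as "Never, Occasional (1 in previous years), Yearly (1 each year in previous years) and Frequent", and has no residual row. The table covers COPD patients in the Full and Sub-cohort populations, in total and by GOLD grade.

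The protocol uses a simpler split. In 5.2, "Exacerbator is a patient who has 1 or more exacerbations in the 2 years before recruitment", and a non-exacerbator has had none in the same two years. Protocol 9.1 collects "Number of exacerbations in the previous 12 months and 24 months", and separately the moderate and severe events over the same two periods.

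**The concern.** SAP 5.4 asks for a number and percentage in each category, so the categories need to be exclusive and to cover everyone. These do not. Frequent looks only at the last 12 months, while Occasional and Yearly cover only totals of one or two over 24 months. Someone whose multiple events fell mainly in the earlier year is caught by neither.

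Either the rows by GOLD grade will not sum to the COPD total, or the programmer must pick a row once the data are in hand, which changes the percentages. The omission is selective, because every omitted patient has at least two events in two years. Any later phenotype analysis that reuses the variable would inherit the gap.

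**Working it through.** **Inputs.** The row definitions come from SAP 17.5.3. Write a history as (a, b), where a is the count in the last 12 months and b the count in the 12 months before. Protocol 9.1 gives both: b is the 24-month count minus the 12-month count. No event rate is given anywhere, and the plan has no figure of its own to reproduce.

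**Step 1: literal reading (Yearly is exactly one in each year).**

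| | b = 0 | b = 1 | b ≥ 2 |
|---|---|---|---|
| a = 0 | Never | Occasional | no row |
| a = 1 | Occasional | Yearly | no row |
| a ≥ 2 | Frequent | Frequent | Frequent |

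The uncovered histories are (0, ≥2) and (1, ≥2). Every other history has exactly one row. This step needs no assumption.

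**Step 2: alternative reading (Yearly is at least one in each year).** (1, ≥2) moves to Yearly. (0, ≥2) still has no row, and every history with a ≥ 2 and b ≥ 1 now sits in both Yearly and Frequent.

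**Step 3: size, under assumed inputs.** Each patient has a personal rate drawn from a gamma distribution with mean m per year and shape s, the same in both years. Counts are Poisson given that rate. Then:

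- literal: U = P(a ≤ 1) − P(0,0) − P(0,1) − P(1,0) − P(1,1)
- alternative: U′ = P(a = 0) − P(0,0) − P(0,1)
- exacerbators: E = 1 − P(0,0)

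Worked case, m = 0.5 and s = 1:

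- P(a=0) = 1/(1+m) = 0.6667
- P(a=1) = m/(1+m)² = 0.2222
- P(0,0) = 1/(1+2m) = 0.5
- P(0,1) = P(1,0) = m/(1+2m)² = 0.125
- P(1,1) = 2m²/(1+2m)³ = 0.0625
- U = 0.8889 − 0.8125 = 0.0764, and U/E = 0.0764/0.5 = 15.3%
- U′ = 0.6667 − 0.5 − 0.125 = 0.0417, and U′/E = 8.3%

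Over the assumed range (each cell: s = 0.5, then s = 1):

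| m per year | Literal, % of COPD | Literal, % of exacerbators | Alternative, % of COPD | Alternative, % of exacerbators |
|---|---|---|---|---|
| 0.1 | 1.0, 0.8 | 6.5, 4.8 | 0.7, 0.6 | 4.7, 3.8 |
| 0.2 | 2.7, 2.5 | 10.7, 8.6 | 1.7, 1.7 | 6.7, 6.0 |
| 0.4 | 5.6, 6.1 | 14.7, 13.7 | 3.0, 3.5 | 7.8, 7.9 |
| 0.5 | 6.6, 7.6 | 15.6, 15.3 | 3.4, 4.2 | 7.9, 8.3 |
| 1.0 | 9.0, 12.0 | 16.3, 18.1 | 4.1, 5.6 | 7.4, 8.3 |

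**Step 4: sensitivity to the model.** Widening the grid to 0.1-2.0 events per year and adding s = 2 and a plain Poisson model takes the literal share of exacerbators from 2.6% (0.1 per year, Poisson) to 26.0% (1.5 per year, Poisson).

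A different anchor is the sub-cohort recruitment target: "About 150 COPD participants with a history of at least 1 exacerbation event(s) within the past 2 years", out of 100 + 100 + 50 = 250 COPD places, or 60%. Setting m so that 60% are exacerbators gives 12-17% of them unclassified, about 18 to 26 of 150. That 60% is a quota, not an estimate for the main cohort.

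**The case against.** A reader might infer that a material share of exacerbators is certain to be lost. The documents do not support that. They give no history distribution, and some of their text points to low rates: the rationale in the Amendment 2 summary says mild-to-moderate patients have fewer treated exacerbations. SAP 13.1 and 17.5.3 do not say whether the phenotype counts all symptom-defined events or only moderate and severe ones, and that choice drives the rate.

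A reader might also take the table for an objective 2 endpoint. Objective 2 does speak of exacerbation phenotypes, but the exacerbator grade is not among its visible listed endpoints (one item is redacted). SAP 2.1 and 13 make the phenotype analysis descriptive only. No model visible in the current SAP uses the four rows: the exacerbation-rate model uses moderate/severe history, the spirometry models use a count, and the subgroup is any versus none.

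The patients are also not lost from the report. SAP 6.4 summarises the number of exacerbations as 0, 1, 2 and more than 2, by GOLD grade.

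All of this stands and limits the importance. None of it closes the gap, because the 6.4 table does not assign anyone a phenotype row. The at-least-one reading of Yearly narrows the gap but creates an overlap. It is also the less natural reading, since in 17.5.3 the at-least sign appears only in the Frequent row.

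**Conclusion.** The concern holds as a definitional gap, which follows from the wording alone on either reading.

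Its size rests on assumed rates and an assumed gamma-Poisson model with shape 0.5-1. At 0.1-1.0 events per year the literal reading leaves about 1-12% of COPD participants and 5-18% of exacerbators without a row. On the planned 1,700 COPD participants that is roughly 0.008 × 1,700 ≈ 14 to 0.12 × 1,700 = 204 people. The alternative reading gives about half the literal share at 0.4-1.0 per year; at 0.1-0.2 per year the reduction is smaller.

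The consequence is limited to a descriptive table by GOLD grade, so this is a minor point that is worth correcting because correction is cheap.

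**What to change.** In both SAP 13.1 and 17.5.3, define the rows on the collected 12- and 24-month counts:

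- **Never:** 0 in 24 months, which matches the protocol's two-year definition of a non-exacerbator.
- **Occasional:** exactly 1 in 24 months.
- **Two or more in 24 months with at most 1 in the last 12:** keep one in each year as the Yearly row, and show the remainder as its own row.
- **Frequent:** 2 or more in the last 12 months.

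State in the same place whether all symptom-defined events or only moderate and severe ones count. Without that, two programmers could still fill the rows differently.

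The cost is SAP wording and one extra row in the table shell. No new data are needed.

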**Microbiome****17.6. Appendix 6: Reporting Standards for Missing Data****17.6.1. Premature Withdrawals**

Element	Reporting Detail
General	
 
Subject study completion (i.e. as specified in the protocol) was defined as completed all scheduled visit and completed exit visit.
 
Withdrawn subjects were not replaced in the study.
 
All available data from participants who were withdrawn from the study will be listed and all available planned data will be included in summary tables and figures, unless otherwise specified.
 
Withdrawal visits will be slotted as per Appendix 3: Assessment Windows or will be summarised as withdrawal visits.
 

**17.6.2. Handling of Missing Data**

Element	Reporting Detail
General	
 
Missing data occurs when any requested data is not provided, leading to blank fields on the collection instrument: 
 
These data will be indicated by the use of a “blank” in subject listing displays. Unless all data for a specific visit are missing in which case the data is excluded from the table.
 
Answers such as “Not applicable” and “Not evaluable” are not considered to be missing data and should be displayed as such.
 
 
 

MAR	
 
The data are said to be missing at random (MAR) when drop-out probability is conditionally independent of missing data given the observed outcomes and covariates
 
There is an underlying assumption that the data are missing at random. Missing data are not explicitly imputed in the Mixed Model Repeated Measures model.
 
If data are MAR, the source of the missing data may be ignored and inference is valid from a mixed-effects model. In other words, it is not necessary to include in the data analysis information about the source of the missing data.
 
For sensitivity analyses, Multiple imputation will be utilized under the assumption of MAR for MMRM model for participants who withdrawal from the study as well as lost to follow up the study, post- withdrawal counts were imputed conditional upon the subject's own observed measurements prior to withdrawal.
 

## 17.7. Appendix 8: Abbreviations & Trademarks

### 17.7.1. Abbreviations

Abbreviation	Description
CAPTURE	COPD Assessment in Primary Care to Identify Undiagnosed Respiratory Disease and Exacerbation Risk
CAT	COPD Assessment Test
CDISC	Clinical Data Interchange Standards Consortium
CID	Clinically Important Deterioration
COPD	Chronic Obstructive Pulmonary Disease
CSR	Clinical Study Report
CTR	Clinical Trial Register
DDA	Digital Data Analytics
DOB	Date of Birth
EXACT	EXAcerbation of COPD Tool
FVC	forced vital capacity
GOLD	Global Initiative for Chronic Obstructive Lung Disease
GSK	GlaxoSmithKline
HRCT	High-resolution computed tomography
ICH	International Conference on Harmonization
IDSL	Integrated Data Standards Library
MMRM	Mixed Model Repeated Measures
PDMP	Protocol Deviation Management Plan
PRO	Patient-reported Outcomes
RAP	reporting and analysis plan
SAC	Statistical Analysis Complete
SGRQ-C	St. George's Respiratory Questionnaire for COPD
SOP	Standard Operation Procedure
TFL	Tables, Figures & Listings
TLC	Total Lung Capacity

**Description:**

- The purpose of this RAP (Core RAP) is to describe the planned analyses and output to be included in the Clinical Study Report (CSR) for Protocol 208630.
- This RAP is intended to describe the planned study population analyses, disease progression analyses, phenotypic analyses, treatment pattern and healthcare resource utilization analyses. This RAP will be provided to the study team members to convey the content of the Statistical Analysis Complete (SAC) deliverable.

**Version history**

RAP Version	Approval Date	Protocol Version (Date) on which RAP is Based	Change	Rationale
RAP	10-Feb-2022	208630 / Amendment 02 (17-Jun-2021)	Not applicable	Original version
RAP amendment1	27-Oct-2022	208630 / Amendment 02 (17-Jun-2021)	Section 2.1: removed 'Per protocol populations were added to analyses populations.'	Correction
			Section 2.1: updated the content of 'treatment pattern, health resource utilization, HRCT, sputum'	Correction 6 months longitudinal data are available and baseline HRCT data are ready, sputum analysis had been done
			Section 3.1 table1: updated the content of Visit 1 to Visit 4	Clarification
			Section 4 table 2: Add HRCT analysis in sub-cohort population	Baseline HRCT data are ready
			Section 5.3.2: Added GOLD II patients in secondary comparison.	Clinical request
			Section 6.1 table 3: updated the content of Computed tomography (Lung HRCT)	Clinical request

## CONFIDENTIAL

The GlaxoSmithKline group of companies

208630

RAP Version	Approval Date	Protocol Version (Date) on which RAP is Based	Change	Rationale
			Section 6.3 removed “Wilcoxon-rank sum test will be used to analyse mMRC dyspnea score among different type of subjects in Full population.”	Clinical request
			Section 7.4.1: updated the sensitivity and specificity analysis of CAPTUR	Clinical request
			Section 9.1: updated the analysis strategy of treatment pattern	Clinical request
			Section 9.2: added Stratified analysis according to COPD and non-COPD patients	Clinical request
RAP amendment2	10 Aug 2023	208630 / Amendment 02 (17-Jun-2021)	Section 7.4.1: added the logistic regression analysis for exacerbation	Clinical request

